#### 17.1 Sample size calculation

The sample size is determined to ensure a sufficient power for the primary analysis. This is determined using a non-inferiority limit of 0.4%.

Protocol  
Trial ID: NN1218-4357  
UTN: U1111-1197-8289

CONFIDENTIAL

Date:  
Version:  
Status:  
Page:

30 November 2020  
5.0  
Final  
80 of 105

Novo Nordisk

In the global phase 3a programme where treatment with faster aspart has been investigated, the completion rates have been high, i.e. approximately 88-94%. Therefore it will not be unexpected that treatment discontinuation might be as low as 10%.

It is expected that a larger portion of the trial population will constitute subjects with T2DM. For these calculations the proportion of subjects with T1DM is assumed to be 20%. Combining expected differences for T1DM and T2DM subjects and weighting by the proportion of expected T1DM subjects we will assume a treatment difference of -0.02% (i.e., in favour of faster aspart).

The power for the primary (non-inferiority) analysis is based on a *t*-statistic under the assumption of a one-sided test of size 2.5 %, a non-inferiority margin of 0.4% and SD of 1.2%. Using these values we get a power of 81.7% for the primary analysis with a sample size of 270. Adjusting further for a dropout rate of approximate 10%, 300 subjects will be randomised.

The power for non-inferiority for scenarios where SD = 1.0% or 1.2% and mean difference of 0.00% or -0.02% based on sample size 270 is shown in Table 17-1.

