#### Primary analysis:

The estimand will be addressed by the primary analysis on all subjects included in the full analysis set and using the data collected from date of first dose of randomised NovoRapid®/faster aspart and to 7 days after the day of last dose of randomised NovoRapid®/faster aspart. Change from baseline in HbA1c after 16 weeks of randomised treatment will be analysed using a mixed-effect model for repeated measurements (MMRM) where all calculated changes in HbA1c from baseline at visits will be included in the analysis. This model will include treatment and stratification (T1DM/T2DM) as fixed factors, HbA1c at baseline as covariate and interactions between all fixed factors and visit. An unstructured covariance matrix will be used to describe the variability for the repeated measurements for a subject. This approach relies on the assumption that data are missing at random (MAR). From this model, the treatment difference after 16 weeks will be estimated with a 95% confidence interval calculated.

Non-inferiority will be considered confirmed if the upper boundary of the two-sided 95% confidence interval is below or equal to 0.4% or equivalent if the *p*-value for the one-sided test of

$$H_0: D > 0.4\% \text{ against } H_A: D \leq 0.4\%,$$

is less than or equal to 2.5%, where *D* is the mean treatment difference (faster aspart minus NovoRapid®).

The trial also aims to confirm the superiority of treatment with faster aspart for the change from baseline HbA1c 16 weeks after randomisation. Here superiority will be based on the same 95% CI that was used for addressing the primary analysis. Superiority will be confirmed if the upper boundary of the two-sided 95% confidence interval of the mean treatment difference is below 0%.

Protocol  
Trial ID: NN1218-4357  
UTN: U1111-1197-8289

CONFIDENTIAL

Date:  
Version:  
Status:  
Page:

30 November 2020  
5.0  
Final  
82 of 105

Novo Nordisk

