## Additional analysis

Differences between the two populations will be investigated further by estimating the treatment differences separately for subjects with T1DM and T2DM. These treatment differences will be estimated based on the same data and a similar statistical model as the primary analysis but including interaction terms between treatment, stratification (T1DM and T2DM), and visit.

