### Sensitivity analysis for the primary analysis addressing the estimand

- 1) A tipping point analysis will be made based on the data and a similar statistical model as the primary analysis addressing the estimand but using multiple imputation. In this analysis observations for subjects with missing values are imputed based on the treatment arm they were randomised to and subjects in the faster aspart group are given a penalty. This is done to investigate the robustness of the conclusion in the primary analysis with respect to the MAR assumption and mimics a scenario where the HbA1c of the subjects in the faster aspart groups evolve less favourably than predicted. As a first step imputations will be done without penalty assuming MAR. Second, the imputed values for week 16 in the faster aspart group will be added a penalty. This is done repeatedly, gradually increasing the penalty until the conclusion from the non-inferiority analysis no longer holds. This will serve as a sensitivity analysis for the non-inferiority analysis and the specific value of the penalty that changes the conclusion will be used to evaluate the robustness of the conclusion of the non-inferiority analysis.
- 2) A tipping point analysis using multiple imputation similar to 1) but with the modification that subjects discontinuing treatment due to non-eligibility (discontinuation due to criteria 1- 4, Section 6.6) in the faster aspart group will not have a penalty added. These analyses are motivated by the fact that data from subjects prematurely discontinuing randomised treatment due to non-eligibility can reasonably be assumed to be missing completely at random.
- 3) The same statistical model using MMRM and data as in the primary analysis, but restricted to the PP analysis set. This analysis will investigate the situation that subjects might have deviated from the inclusion and exclusion criteria and will serve as sensitivity analysis for the non-inferiority analysis.

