### **Change from baseline in FPG to 16 weeks after randomisation**

Change from baseline in FPG to 16 weeks after randomisation will be analysed based on all planned post baseline measurements until or at 16 weeks after randomisation using a model similar to the primary analysis except with baseline FPG as covariate.

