### **Change from baseline in endpoints derived from the 7-9-7-point SMPG profile to 16 weeks after randomisation**

In general, analyses will be based on the entire 7-9-7-point SMPG profile.

Protocol  
Trial ID: NN1218-4357  
UTN: U1111-1197-8289

CONFIDENTIAL

Date:  
Version:  
Status:  
Page:

30 November 2020  
5.0  
Final  
84 of 105

Novo Nordisk

PPG and PPG increments based on the 7-9-7-point SMPG profiles will be derived separately for PG measurements made 1 hour after the meal. In the following section this distinction will be considered implicit and without further explanation.

Pre-prandial PG and PPG will be recorded by the subjects as part of the 7-9-7-point SMPG profile prior to three defined visits. Individual mean mealtime PPG (post-breakfast, post-lunch, post-main evening meal) will be derived from the three profiles. Overall mean PPG will be derived from the individual derived mealtime PPG values.

PPG increment for each meal (breakfast, lunch, main evening meal) will be derived from the 7-9-7-point SMPG profile as the difference between PPG values and the PG value before meal in each separate profile. The mean of the derived increments will then be calculated separately for each meal. Mean 1-hour PPG increments over all meals will be derived as the mean of all corresponding mean meal increments.

- Change from baseline in mean of the 7-9-7-point SMPG profile

The mean of the 7-9-7-point SMPG profile is defined as the area under the curve (AUC) profile divided by the measurement time, and is calculated using the linear trapezoidal technique.

Change from baseline in the mean of the 7-9-7-point SMPG profile 16 weeks after randomisation will be analysed based on all planned post baseline measurements until or at 16 weeks after randomisation using a model similar to the primary analysis except with the corresponding baseline value as covariate.

- Change from baseline in 1-hour PPG and PPG increment (mean, breakfast, lunch and main evening meal)

Change from baseline in 1-hour PPG and PPG increment endpoints 16 weeks after randomisation for mean over all three meals and the individual meals will be analysed separately based on all planned post baseline measurements until or at 16 weeks after randomisation using a model similar to the primary analysis except with the corresponding baseline value as covariate.

- Fluctuation in 7-9-7-point SMPG profile

The fluctuation in the 7-9-7-point SMPG profile is defined as:

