4.5 Changes to Protocol-planned Analysis

No change to the protocol.

5 Sample size determination

The sample size is determined to ensure a sufficient power for the primary analysis. This is determined using a non-inferiority limit of 0.4%.

In the global phase 3a programme where treatment with faster aspart has been investigated, the completion rates have been high, i.e. approximately 88-94%. Therefore it will not be unexpected that treatment discontinuation might be as low as 10%.

It is expected that a larger portion of the trial population will constitute subjects with T2DM. For these calculations the proportion of subjects with T1DM is assumed to be at least 20%. Combining expected differences for T1DM and T2DM subjects and weighting by the proportion of expected T1DM subjects we will assume a treatment difference of -0.02% (i.e., in favour of faster aspart).

The power for the primary (non-inferiority) analysis is based on a *t*-statistic under the assumption of a one-sided test of size 2.5 %, a non-inferiority margin of 0.4% and SD of 1.2%. Using these values we get a power of 81.7% for the primary analysis with a sample size of 270. Adjusting further for a dropout rate of approximate 10%, 300 subjects will be randomised.

The power for non-inferiority for scenarios where SD = 1.0% or 1.2% and mean difference of 0.00% or -0.02% based on sample size 270 is shown in [Table 5-1](#).

Table 5-1 The power for non-inferiority for different scenarios

Power for non-inferiority	Treatment difference = 0%	Treatment difference = -0.02%
SD = 1.0%	90.6%	93.0%
SD = 1.2%	77.9%	81.7%

The power calculation is done using proc power in SAS Version 9.4.

6 References

1. ICH Harmonised Tripartite Guideline. Statistical Principles for Clinical Trials E9, Current step 4 version. 5 Feb 1998.

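### Read literally, the primary MMRM gives baseline HbA1c one slope across visits; crossing it with visit is a cheap clarification that protects week-16 precision if slopes differ

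*Protocol*

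**What the plan says.** The primary analysis in protocol 17.3 describes the MMRM in one sentence. It begins "This model will include treatment and stratification (T1DM/T2DM) as fixed factors" and continues with HbA1c "at baseline as covariate and interactions between all fixed factors and visit". The covariance is unstructured, and the week-16 treatment difference with its 95% CI decides both non-inferiority and superiority.

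SAP 4.3.2 repeats the sentence, and SAP 4.5 states "No change to the protocol". Neither document names a baseline-by-visit term anywhere.

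Other analyses lean on this model:
- The separate T1DM and T2DM estimates use "a similar statistical model as the primary analysis but including interaction terms between treatment, stratification (T1DM and T2DM), and visit", which is silent on baseline.
- FPG is analysed "using a model similar to the primary analysis except with baseline FPG as covariate". The SMPG, lipid and body-weight analyses are worded in the same way.
- For the tipping-point analysis, the text says that "observations for subjects with missing values are imputed based on the treatment arm they were randomised to", but the imputation model is not written out.

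Protocol 17.1 bases the 81.7% power on a t-statistic with "a non-inferiority margin of 0.4% and SD of 1.2" (both in % HbA1c). It does not say whether that SD is before or after baseline adjustment.

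**The concern.** The sentence puts baseline HbA1c outside the fixed factors and crosses only the fixed factors with visit. Taken at its word, one baseline coefficient serves every post-baseline visit.

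HbA1c responds slowly, so the relation between baseline and change could strengthen over 16 weeks. The documents neither show nor exclude this. If it does, the common coefficient is a compromise across visits, and the week-16 contrast is adjusted with the wrong slope.

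What is at stake is precision at the deciding visit and clarity about which model is primary. Two competent programmers could fit different models from this sentence.

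**Working it through.** **1. Reproduce the plan.** Noncentral t, 135 per arm, one-sided 2.5%, margin 0.4, difference -0.02: SD 1.2 gives 81.73% and SD 1.0 gives 93.03%. With no true difference the results are 77.9% and 90.6%. All four cells of Table 17-1 match.

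**2. Mechanism.** Treatment is crossed with visit. With complete data and a given common slope b, the week-16 estimate is therefore the difference in mean change minus b times the baseline difference. The covariance matrix affects b but does not make it visit-specific. Hence:
- crossed model: variance proportional to s² = 1.2² - β16² × Var(baseline)
- common slope: variance proportional to s² + (β16 - b)² × Var(baseline)

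Here β16 is the week-16 slope and b is the generalised least squares compromise. The first line reads 1.2% as the unadjusted SD.

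**3. Assumed inputs (not in the documents).** 2 to 4 post-baseline visits; baseline SD 0.6 to 0.8; β16 from -0.3 to -0.5; slopes linear in visit; compound-symmetric or AR(1) correlation of 0.5, 0.75 or 0.9; first-visit residual SD 44%, 75% or 100% of the week-16 value. The gap is the difference between the first-visit and week-16 slopes. Across the grid, |β16 - b| is 0.50 times the gap at its mildest. At its worst it is 1.035, 1.276 and 1.578 times the gap at correlations 0.5, 0.75 and 0.9.

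**4. Worked worst corner** (β16 = -0.4, baseline SD 0.8, gap 0.25, correlation 0.9). s² = 1.44 - 0.16 × 0.64 = 1.3376. The added term is (1.578 × 0.25)² × 0.64 = 0.0996. The ratio is 1.4372/1.3376 = 1.0745. The SDs are 1.157 (crossed) and 1.199 (common).

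| Correlation (β16 -0.4, baseline SD 0.8, gap 0.25, worst corner) | Variance ratio | Power, common | Power, crossed |
|---|---|---|---|
| 0.5 | 1.032 | 83.3% | 84.4% |
| 0.75 | 1.049 | 82.7% | 84.4% |
| 0.9 | 1.0745 | 81.8% | 84.4% |

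**5. Range over the grid.** Equal slopes: no loss. Gap 0.1: about 0.1 to 1.3% extra variance. Gap 0.25: about 0.4 to 8%, at most about 2.6 power points.

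**6. Lowest power.** β16 = -0.3, baseline SD 0.8, gap 0.25, correlation 0.9: s² = 1.44 - 0.09 × 0.64 = 1.3824. Adding 0.0996 gives 1.4820 (SD 1.217) and power 80.6%, against 83.3% crossed. At correlation 0.75 the worst case is 81.5 to 81.6%, against 82.6 to 83.3%.

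**7. If 1.2% is already a residual SD.** The crossed model has 81.7%. A common slope at gap 0.25 gives 80.0 to 81.6% at correlation 0.75. The worst corner at 0.9 has SD √(1.44 + 0.0996) = 1.241 and power 79.1%.

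**8. Break-even with no baseline adjustment** (β16 = -0.4, worst corner): 0.4/1.578 = 0.25, 0.4/1.276 = 0.31 and 0.4/1.035 = 0.39 at correlations 0.9, 0.75 and 0.5.

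**9. Simulation checks.** MMRM fits with 300 randomised, about 10% dropout, four visits, correlation 0.8, baseline SD 0.8 and slopes from -0.15 to -0.50 (800 runs) gave mean SE 0.1395 (common) against 0.1353 (crossed), with negligible bias. With equal slopes both gave 0.1347. A separate 20,000-run check with complete data (gap 0.25, worst corner at correlation 0.75, baseline SD 0.8) gave a variance ratio of 1.051, power of 82.3% against 84.3%, and 0.951 coverage for the common-slope CI.

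**The case against.** The strongest reply is that no error is shown. The sentence is prose rather than a full model statement; it also omits the visit main effect, which any MMRM of this kind needs. If the sponsor used fixed factors to mean all fixed effects, the crossed model is already the plan. That stands, and it is why the point is a clarification. It does not remove the need, because nothing in the SAP settles which model is meant.

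It is also true that every magnitude is assumed. The documents give no baseline SD, slopes or correlation, and the HbA1c visit schedule is not legible in the text available. No passage suggests that slopes differ, and at a gap of 0.1 the effect is trivial.

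A reader might infer that the primary test is biased or invalid. It is not: randomisation protects the estimate, a common slope is a legitimate choice, and simulated coverage was nominal. A reader might also infer that the planned power is undermined, or equally that it is safe. Protocol 17.1 supports neither flatly, since it does not define the SD. Nor is there one slope gap beyond which the common slope does harm; the break-even moves with the correlation.

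**Conclusion.** The point holds as a minor, conditional one. On the literal reading the primary model has one baseline slope. If slopes vary by visit, part of the week-16 gain from baseline adjustment is lost; if they do not, nothing is lost.

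With gaps up to 0.25 and the inputs listed, the loss is 0 to about 2.6 power points. Larger gaps cost more: for slopes from -0.15 to -0.50 (baseline SD 0.8, correlation 0.9), power was 82.6% against 86.0%. In most scenarios power with a common slope still exceeds 81.7%. It can fall to about 80.6% with a shallow week-16 slope and high correlation, and it also falls below 81.7% if 1.2% is already a residual SD.

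The crossed model recovers the full gain from linear adjustment with one slope per visit shared by T1DM and T2DM. It makes no claim about slopes that differ by diabetes type.

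**What to change.** Before unblinding, state the primary model in full: visit, treatment, diabetes type and baseline HbA1c, with visit interactions for treatment, diabetes type and baseline HbA1c, and unstructured covariance.

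Use the same mean model in the T1DM/T2DM analysis and in those models described as similar that have more than one post-baseline visit. SMPG values are recorded "as part of the 7-9-7-point SMPG profile prior to three defined visits", which leaves two post-baseline visits if one of the three is baseline. When the tipping-point imputation model is written, let its baseline coefficient vary by visit.

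The wording change is a few words in protocol 17.3 and SAP 4.3.2. It must be recorded, either in SAP 4.5, which now reports no change, or by protocol amendment. Protocol section 17 lets the SAP be finalised up to database lock. The statistical cost is (visits minus 1) parameters, so 1 to 3 for 2 to 4 visits, with no measurable loss of precision when slopes are equal. No extra subjects, data or alpha are needed. If the term was always intended, the edit simply documents it.

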## Additional analysis

Differences between the two populations will be investigated further by estimating the treatment differences separately for subjects with T1DM and T2DM. These treatment differences will be estimated based on the same data and a similar statistical model as the primary analysis but including interaction terms between treatment, stratification (T1DM and T2DM), and visit.

### Sensitivity analysis for the primary analysis addressing the estimand

- 1) A tipping point analysis will be made based on the data and a similar statistical model as the primary analysis addressing the estimand but using multiple imputation. In this analysis observations for subjects with missing values are imputed based on the treatment arm they were randomised to and subjects in the faster aspart group are given a penalty. This is done to investigate the robustness of the conclusion in the primary analysis with respect to the MAR assumption and mimics a scenario where the HbA1c of the subjects in the faster aspart groups evolve less favourably than predicted. As a first step imputations will be done without penalty assuming MAR. Second, the imputed values for week 16 in the faster aspart group will be added a penalty. This is done repeatedly, gradually increasing the penalty until the conclusion from the non-inferiority analysis no longer holds. This will serve as a sensitivity analysis for the non-inferiority analysis and the specific value of the penalty that changes the conclusion will be used to evaluate the robustness of the conclusion of the non-inferiority analysis.
- 2) A tipping point analysis using multiple imputation similar to 1) but with the modification that subjects discontinuing treatment due to non-eligibility (discontinuation due to criteria 1- 4, Section 6.6) in the faster aspart group will not have a penalty added. These analyses are motivated by the fact that data from subjects prematurely discontinuing randomised treatment due to non-eligibility can reasonably be assumed to be missing completely at random.
- 3) The same statistical model using MMRM and data as in the primary analysis, but restricted to the PP analysis set. This analysis will investigate the situation that subjects might have deviated from the inclusion and exclusion criteria and will serve as sensitivity analysis for the non-inferiority analysis.

## 17.4 Secondary endpoints

### 17.4.1 Supportive secondary endpoints

#### 17.4.1.1 Efficacy endpoints

All endpoints except insulin dose in this section will be assessed using the FAS. Insulin dose will be presented using the safety analysis set.

Protocol  
Trial ID: NN1218-4357  
UTN: U1111-1197-8289

CONFIDENTIAL

Date:  
Version:  
Status:  
Page:

30 November 2020  
5.0  
Final  
83 of 105

Novo Nordisk

### **Change from baseline in 30- minutes, 1- hour, 2- hour, and 3- hour PPG increment and 30- minutes, 1- hour, 2- hour, and 3- hour PPG to 16 weeks after randomisation (meal test)**

Laboratory measured PG from the meal test will be analysed for 30 minutes, 1-hour, 2-hours, and 3-hours PPG separately. The corresponding PPG increments will be derived separately using each PPG measurement minus the pre-prandial PG measurement.

Change from baseline in PPG and PPG increment endpoints 16 weeks after randomisation will be analysed based on the FAS using an ANOVA model including treatment and stratification (T1DM/T2DM) as factors, and with the corresponding baseline value as covariate.

### **Change from baseline in FPG to 16 weeks after randomisation**

Change from baseline in FPG to 16 weeks after randomisation will be analysed based on all planned post baseline measurements until or at 16 weeks after randomisation using a model similar to the primary analysis except with baseline FPG as covariate.

### **If a subject achieves HbA1c target 16 weeks after randomisation**

#### **HbA1c < 7.0%**

A dichotomous (responder/non-responder) endpoint will be defined based on whether a subject has met the HbA1c target (HbA1c < 7.0%) 16 weeks after randomisation.

This responder endpoint will be analysed based on a logistic regression model using treatment and stratification (T1DM/T2DM) as factors, and baseline HbA1c as covariate. In the analysis, subjects who prematurely discontinue trial product and subjects with missing HbA1c at 16 weeks will be included as non-responders.

#### **HbA1c < 7.0% without severe hypoglycaemia**

A dichotomous (responder/non-responder) endpoint will be defined based on whether a subject has met the HbA1c target (HbA1c < 7.0%) 16 weeks after randomisation without treatment emergent severe hypoglycaemic episodes.

This responder endpoint will be analysed based on a logistic regression model using treatment and stratification (T1DM/T2DM) as factors and baseline HbA1c as covariate. In the analysis, subjects who prematurely discontinue trial product and subjects with missing HbA1c at 16 weeks will be included as non-responders.

